#### 10.1.2 Interpretation of data

The Kolmogorov-Smirnov tests will be carried out to know if the distribution presents normality in the results obtained in each study group. [fifty]

The results of the continuous quantitative variables will be presented in measures of central tendency: mean, standard deviation and ranges.

The statistical analysis of the continuous quantitative variables to find significant differences (p < 0.05) will be as follows:

- Intra-group analysis: they will be determined using the Wilcoxon rank test for quantitative variables. [51]
- •
- Between-group analysis: The differences between the groups will be analyzed using the Mann-Whitney U test.

The level of difference to consider significance will be an alpha ( $\alpha$ ) of 0.05 or less.

The result of the nominal and ordinal qualitative variables will be presented in frequencies, proportions and percentages.

The statistical analysis to identify significant differences of the qualitative variables will be carried out by creating 2x2 contingency tables and will be carried out as follows:

- Intragroup difference: McNemar test. [52] Which is applied to 2 × 2 contingency tables with a dichotomous trait, with pairs of matched subjects, to determine if the marginal frequencies of row and column are equal (marginal homogeneity).
- Difference between groups: Pearson's Chi-square test (X2) or Fisher's exact test in expected values less than 5.

The level of difference to consider significance will be an alpha ( $\alpha$ ) of 0.05 or less.

For the reporting of adverse events, all the eyes of those participants who were randomly assigned to an intervention group after the baseline visit will be considered. The results will be expressed in number of subjects.

The final report of the results will be shown in tables or graphs, as appropriate.

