#### 7.3.2 Secundary outcome variables

- -Changes in the BCVA (TE: day 8).
- -Changes in corneal and conjunctival staining with lysamine green (TE: 8).
- -Changes in corneal and conjunctival staining with fluorescein (TE: day 8).
- -Conjunctival hyperemia changes (TE: day 8).
- -Incidence of chemosis (TE: day 8)

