#### 7.3.3 Definition of variables, methods and scales to be used for their measurement

Variable	Туре	Unit (Symbol)	Method of measurement	normal value	evaluation time	statistical test
Primary						
Adverse events	Discreet	Number of cases (n)	Counting	0	VB, V1, VF y LLS	U de Mann- Whitney
events	Categoric al nominal	Present/ absent	Observation	Absent	LLS	χ2 or exact by Fisher
Score of	Discreet	Points	Questionnaire	NA	VB, VF	U de Mann- Whitney
Secondary						
MAVC	Discreet	Fraction	Poster of Snellen	1	VB, V1 y VF	U de Mann- Whitney
Corneal and conjunctival fluorescein staining	Ordinal	Levels	Direct observation with slit lamp and cobalt blue filter, Oxford scale graduation	0	VB, V1 y VF	χ2 or exact by Fisher
Corneal and conjunctival staining with lysamine green	Ordinal	Levels	Direct observation with slit lamp, Oxford scale graduation	0	VB, V1 y VF	χ2 or exact by Fisher
Conjunctiv al hyperemia	Ordinal	Normal / Very Mild / Mild / Moderate / Severe	Direct observation. Clasification of Efron.	Normal	VB, V1 y VF	χ2 or exact by Fisher
Chemosis	Categorical nominal	Present / absent		Absent	VB, V1 y VF	χ2 or exact by Fisher

Table 2. Defoperational definition of variables

The variables, the method and scales for their measurement are described in detail below. They are in order according to Table 2

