# 15.2 Oxford scale

PANEL	Grade	Criteria
A	0	Equal to or less than panel A
В	l	Equal to or less than panel B, greater than A
С	Ш	Equal or less than panel C, greater than B
D	III	Equal to or less than panel D, greater than C
E	IV	Equal to or less than panel E, greater than D
>E	V	Greater than panel E

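### The six-level Oxford and five-level Efron grades are to be tested in 2x2 tables with no cut-point given, so the tests for three of the five secondary safety outcomes are undefined as written.

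*Combined protocol and SAP*

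**What the plan says.** Section 10.1.2 treats ordinal and nominal variables together: "The result of the nominal and ordinal qualitative variables will be presented in frequencies, proportions and percentages". It then fixes the format of the tests: "The statistical analysis to identify significant differences of the qualitative variables will be carried out by creating 2x2 contingency tables". Two tests follow.

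- Within arm: "Intragroup difference: McNemar test". The section describes its own requirement: "Which is applied to 2 × 2 contingency tables with a dichotomous trait, with pairs of matched subjects".
- Between arms: "Pearson's Chi-square test (X2) or Fisher's exact test in expected values less than 5".

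Table 2 in section 7.3.3 types both stainings and hyperaemia as ordinal and assigns chi-square or Fisher to each. The Oxford scale in Annex 15.2 has grades 0 to V, the last being "Greater than panel E". Table 2 gives hyperaemia the levels "Normal / Very Mild / Mild / Moderate / Severe". Section 7.3.2 names these outcomes as changes, for example "Conjunctival hyperemia changes (TE: day 8".

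Mann-Whitney and Wilcoxon are reserved in 10.1.2 for quantitative variables.

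**The concern.** A 2x2 table needs two categories. The plan supplies six or five and does not say how to combine them. It also does not define change for a grade: any worsening, a shift of one grade or more, or a move past a threshold would all fit the text.

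Two things are at stake. First, whoever runs the analysis has to pick the split, and different splits of the same data can give different answers. Second, a split ignores the ordering above and below it, which costs power in a trial with only 17 subjects per arm. The outcomes affected are three of the five secondary ones, each with its own safety-comparison objective.

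**Working it through.** **No figure in the plan to reproduce.** The only computed sample size (section 10.2) concerns adverse-event proportions. No power is stated for the graded outcomes.

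**Inputs from the documents.** 17 evaluable subjects per arm; alpha 0.05; Oxford six grades; Efron five levels (numbered 0 to 4 here); chi-square, or Fisher when expected counts fall below 5.

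**Assumptions, because the documents give no grade distribution.** Control arm: Oxford 0.55/0.28/0.12/0.03/0.015/0.005; Efron 0.45/0.35/0.14/0.05/0.01. One day-8 grade per subject; two-sided tests; a common odds ratio (OR) for worsening.

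**Step 1: is a cut stated anywhere?** Six grades allow five cuts and five levels allow four. Sections 7.3.3.4 to 7.3.3.6 set grade III (corneal staining) and grade 3 (hyperaemia) as thresholds for handling a finding as an adverse event. Table 2 has a normal-value column (0, or Normal). Neither is declared as the analysis cut.

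**Step 2: can the cut decide the result?** Take 17 subjects per arm with grades 0/1/2 in numbers 6/8/3 and 5/3/9. Both cuts have expected counts of at least 5, so the plan's rule selects chi-square = N(ad − bc)²/(product of margins).

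- Cut ≥1: 11/17 v 12/17. 34 × (11×5 − 6×12)²/(17×17×23×11) = 9,826/73,117 = 0.13, p = 0.71.
- Cut ≥2: 3/17 v 9/17. 34 × (3×8 − 14×9)²/(17×17×12×22) = 353,736/76,296 = 4.64, p = 0.03.

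Mann-Whitney on the full grades gives p = 0.15.

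**Step 3: information kept by one cut.** Under proportional odds and for small effects, the share kept is 3c(1 − c)/(1 − Σp³), where c is the proportion below the cut.

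- Oxford: 1 − Σp³ = 0.810. Cut ≥1: 3×0.55×0.45/0.810 = 92%. Cut ≥2: 3×0.83×0.17/0.810 = 52%. Cut ≥3: 3×0.95×0.05/0.810 = 18%.
- Efron: 1 − Σp³ = 0.863. Cut ≥1: 3×0.45×0.55/0.863 = 86%. Cut ≥2: 3×0.80×0.20/0.863 = 56%. Cut ≥3: 3×0.94×0.06/0.863 = 20%.

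Other plausible skewed distributions give, for Oxford, 83-99%, 29-55% and 6-16% at the same three cuts, and for Efron 56-90%, 46-74% and 10-17%.

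**Step 4: power at an OR of 4.** The proportion below a cut in the worse arm is c/(c + 4(1 − c)). For Oxford, the proportions at or above cuts 1, 2 and 3 go from 45%, 17% and 5% to 77%, 45% and 17%. Simulated power, using uncorrected chi-square when all expected counts are at least 5 and Fisher otherwise:

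| Test | Power, both scales |
|---|---|
| Mann-Whitney on grades | 56-58% |
| Plan's rule, cut ≥1 | 40-50% |
| Plan's rule, cut ≥2 | 40-46% |
| Plan's rule, cut ≥3 | 8-11% |
| Chi-square on the 2xk table | 31-34% |

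At an OR of 6, Mann-Whitney reaches 77-78%. The plan's rule gives 66% and 64% (Oxford) and 53% and 69% (Efron) at cuts ≥1 and ≥2.

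**Step 5: the adverse-event threshold as a cut.** With none of 17 at or above grade 3 in one arm, Fisher needs 5 of 17 in the other (p = 0.044; with 4, p = 0.103).

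**The case against.** The strongest reply is that the plan already points to workable tests. The normal-value column suggests a split into normal and abnormal, the adverse-event thresholds suggest another, and Table 2 read alone permits a 2xk table with no cut. These are reasonable candidates, but there are several of them and the plan picks none. The staining thresholds name only corneal stains, while the outcome covers cornea and conjunctiva. The 2xk reading conflicts with the 2x2 wording and with McNemar as described, and it ignores grade order.

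Other points on that side do stand.

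- A reader might infer that dichotomising discards most of the information. The documents do not support that: step 3 shows most is lost only at high cuts, and the true grade distribution is unknown.
- A calculation using Fisher at every cut would give 27-37% power at cuts ≥1 and ≥2 for an OR of 4. That overstates the gap, because the plan's rule often selects chi-square there and part of the shortfall is Fisher's conservatism.
- A reader might infer that a missed difference here would be read as proof of safety. Section 10.1.5 confines its no-difference rule to the primary outcomes. Marked grades also reach the primary adverse-event outcome through the thresholds above.
- McNemar does analyse paired change within arm once a cut exists. The objection about change applies between arms.
- Section 10.1.1 blinds the analysts to group, which reduces, though does not remove, the risk of a cut chosen to suit the data.

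**Conclusion.** The concern holds in this form: the prescribed tests for fluorescein staining, lissamine green staining and hyperaemia cannot be run without a choice the plan does not make. That choice can change the answer, and a between-arm 2x2 of day-8 grades does not address change. This rests on the text alone.

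The loss of power is real but conditional. Mann-Whitney was ahead at every cut tested: modestly to clearly at ≥1 and ≥2, heavily at ≥3. Those figures depend on the assumed distributions, a proportional-odds shift and one day-8 grade per subject. Baseline, change and correlation between eyes were not modelled, so they illustrate the cost of cutting and are not the power of the recommended analysis. The consequence is limited to supporting safety comparisons.

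**What to change.** In Table 2 and section 10.1.2, analyse the three outcomes as ordinal change from baseline to day 8, with one pre-specified value per subject. The worse eye is one option; what matters is that the rule is written down. Use the Wilcoxon-Mann-Whitney test (exact or tie-corrected) between arms and the Wilcoxon signed-rank test within arm. Signed-rank treats grade steps as comparable, which should be acknowledged.

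Keep the 2x2 tests for chemosis and for adverse events present or absent. If a dichotomised summary of the grades is also wanted, state its cut and its definition of change in advance. Stating a cut would by itself make the 2x2 tests runnable, but it would still ignore grade order on each side of the cut.

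The cost is SAP wording only. Both tests are already in the plan, and no extra subjects, visits or measurements are needed.

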#### 10.1.3 Procedure for handling missing data

The safety evaluation will include in the analysis all those subjects (both eyes), who have been exposed at least once to any of the interventions, regardless of the visit in which they were eliminated from the study (ITT, intention-to-treat population).

#### 10.1.4 Deviations from the statistical analysis plan

According to the calculation of the sample size to meet the objective of the study, 34 evaluable subjects (17 subjects per arm / both eyes) are required. If this number is not met due to the loss of subjects greater than 20% contemplated in this protocol (loss of follow-up or withdrawal of ICF), in order to balance the treatment groups, the sponsor may substitute these subjects.

The results obtained from the substituted subjects will continue to be used for the safety analysis and will be part of the ITT.

#### 10.1.5 Subjects included in the analysis

Those subjects who comply with an adherence ≥75% will be included in the statistical analysis to fulfill the objective of the study, taken from the subject's diary.

The investigational drug will be considered safe and effective when there are no clinical and statistical differences in all the primary outcome variables, with respect to its comparator (Lagricel® Ofteno, unit dose).

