#### 2.3.4 Hypotheses

H0 = Lagricel® Ofteno multi-dose ophthalmic solution has a safety and tolerability profile similar to Lagricel® Ofteno single-dose in healthy subjects.

H1 = Lagricel® Ofteno multi-dose ophthalmic solution has a different safety and tolerability profile than Lagricel® Ofteno single-dose in healthy subjects

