#### 10.2.2 Justification of the sample calculation

Although there are no references on the calculation of the sample size in phase I studies, it was considered pertinent to perform it according to the safety results of a phase I study, carried out with three ocular lubricants (Humylub Ofteno® PF, Xyel® Ofteno and Systane® Ultra). [53]

The reference study was a single-center, randomized, 1: 1: 1, parallel group, blinded clinical trial. In total, 30 ophthalmologically and clinically healthy subjects were enrolled and included in the safety analyzes.

PRO-037 (Lagricel® Ofteno, multi-dose) is expected to be not inferior to its comparator (Lagricel® Ofteno, single-dose), based on the following working hypotheses:

$$H_0: \varepsilon > \delta$$

$$H_0: \varepsilon \leq \delta$$

Where  $\mu A - \mu B = \epsilon$ , the true difference of the means between the test treatment (Lagricel® Ofteno, multi-dose) and the active control (Lagricel® Ofteno unit-dose). Where  $\delta$  is the margin of non-inferiority, and the relationship between the sample sizes of the two groups is given by:

$$k = \frac{n_A}{n_B}$$

The calculations were made using the equation for two proportions, considering a power of 80% ( $\beta$ ), a significance level of 0.05 ( $\alpha$ ) and a non-inferiority margin ( $\delta$ ) of 5%. [54]

$$n_B = (\frac{p_A(1-p_A)}{k} + p_B(1-p_B))(\frac{z_{1-\alpha} + z_{1-\beta}}{k})^2$$

$$p_A - p_B - \delta$$

In the reference study, after 10 days of treatment (1 drop / 4 times a day), 28 AE were reported in 14 subjects out of a total of 30 subjects exposed to any of the three interventions (46.67%). Without observing statistical differences in the incidence of AE between the three treatment arms (p = 0.788), 19 of the AE were ocular, where burning was the most common, followed by pruritus. Other ocular AE reported were discharge, SCE, and dry eye sensation.

The percentage of ocular AE reported in the study was considered, with respect to the total AE for the three treatments. As it is an ocular lubricant, a similar proportion of ocular AE is expected in ophthalmologically and clinically healthy subjects (50%).

The calculated sample was 56 eyes (28 eyes / arm; 14 subjects / arm), increasing the calculation by 20% considering possible losses, 17 subjects / arm (both eyes) are estimated.

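### The success rule in section 10.1.5 treats non-significant difference tests at 17 subjects per arm as proof that the product is safe and effective

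*Combined protocol and SAP*

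**What the plan says.** The only success criterion is in section 10.1.5: "The investigational drug will be considered safe and effective when there are no clinical and statistical differences in all the primary outcome variables". Section 7.3.1 lists the primary outcomes as AE incidence (days 8 and 10) and the ICO score (day 8).

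The hypotheses in sections 1.1 and 2.3.4 make similarity the null: "H0 = Lagricel® Ofteno multi-dose ophthalmic solution has a safety and tolerability profile similar to Lagricel® Ofteno single-dose in healthy subjects". The alternative is that the profiles differ.

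Sections 1.1 and 10.1.2 and Table 2 (section 7.3.3) plan only tests of difference between groups, at 0.05. For quantitative variables, "The differences between the groups will be analyzed using the Mann-Whitney U test". Qualitative variables get chi-square, or Fisher's exact test when expected counts are below 5. Table 2 applies Mann-Whitney to AE counts and ICO, and chi-square or Fisher to AE presence. Descriptive summaries are also planned, but no interval for a between-group difference and no margin-based test.

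Section 10.2.2 uses a different framework. There the product "is expected to be not inferior to its comparator", and the calculation takes 80% power, a significance level of 0.05 "and a non-inferiority margin" of 5% on a proportion. Neither the analysis section nor the decision rule mentions that margin, and no margin is given for ICO.

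**The concern.** A non-significant difference test shows that the data did not rule out equality. It does not show that the arms are alike, and it becomes easier to obtain as the trial gets smaller. With similarity as the null, section 10.1.5 turns failure to reject into the trial's headline conclusion.

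The rule also requires no clinical difference, but nothing says what size of difference in AE incidence or ICO would count. The cut-offs in sections 7.3.3.3 to 7.3.3.7 (Snellen lines, staining grade, hyperemia grade, chemosis) define an AE in one subject, not a difference between arms. Section 7.3.3.2 says that an ICO score alone is not an AE. The clinical part is thus left to judgement after the data are seen.

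The plan therefore sizes the trial for non-inferiority, tests for a difference and concludes similarity. It also concludes effectiveness. Sections 2.6 and 6.4 mention efficacy, but the objective is safety and tolerability in healthy subjects, and no efficacy objective or endpoint exists.

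**Working it through.** **Inputs.**
- 17 subjects per arm (sections 1.1 and 10.2.1). Section 10.1.3 keeps every exposed subject in the safety analysis, "regardless of the visit in which they were eliminated from the study".
- Two-sided 0.05. The plan gives 0.05 but not the sidedness.
- Comparator AE incidence of 50% at subject level. This is an assumption: the reference study in section 10.2.2 had 14/30 = 46.67%, and the plan's own 50% refers to ocular AEs.
- Subject as unit, because section 10.1.2 says of AEs: "The results will be expressed in number of subjects".

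**The plan's own figure.** Section 10.2.2 gives 28 eyes per arm. With 50% in both arms, its formula gives

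n = [p_A(1−p_A) + p_B(1−p_B)] × (z₁₋α + z₁₋β)² / (p_A − p_B − δ)² = 0.5 × (1.645 + 0.842)² / 0.05² = 1,236.5 (with unrounded z), so 1,237 per arm.

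The stated size does not follow from these inputs. Only the step for losses does: 14 × 1.2 = 16.8, rounded to 17. The trial was therefore not sized to support a conclusion against the 5% margin.

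**Chance that the AE present/absent test is non-significant.** Sum Bin(x; 17, p_test) × Bin(y; 17, p_control) over all tables with p > 0.05.

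| True rates, control vs test | Chi-square, Fisher if expected <5 | Fisher always |
|---|---|---|
| 50% vs 50% | 94% | 98% |
| 50% vs 70% | 77% | 86% |
| 50% vs 80% | 55% | 68% |
| 50% vs 90% | 28% | 37% |
| 46.67% vs 66.67% | 77% | 86% |
| 46.67% vs 76.67% | 55% | 69% |

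**All primary tests together.** The full statistical criterion also needs non-significant AE counts and ICO. This was simulated with assumed distributions: affected subjects have 1 + Poisson(1) AEs, and ICO is normal and independent of AEs. The ranges run from the chi-square rule to Fisher always.
- 50% vs 70%, identical ICO: 71% to 76% of trials pass.
- 50% vs 70%, 0.5 SD ICO difference: 53% to 57%.
- 50% vs 80%, identical ICO: 49% to 56%.

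**A single result.** Take 13/17 (76%) on multi-dose and 8/17 (47%) on single-dose.
- Difference: 5/17 = 29 points. Pooled rate: 21/34 = 0.618.
- Chi-square = 0.294² / (0.618 × 0.382 × 2/17) = 3.11, p = 0.078. Fisher p = 0.157.
- Newcombe 95% interval: −3 to +55 points.

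**Equal observed rates.** 8/17 vs 8/17 gives a Newcombe 95% interval of ±30 points. The normal approximation at 50% gives 1.96 × √(0.5/17) = ±34 points. Even a null result leaves an excess of about six times the 5-point margin open.

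**Sensitivity to the unit.** Section 10.1.2 also says "For the reporting of adverse events, all the eyes of those participants who were randomly assigned to an intervention group" will be considered. If eyes were tested as independent (34 per arm) with both eyes of a subject alike, the AE test would be non-significant in 54% to 64% of trials at a true 70% and 28% to 38% at 80%. The example becomes 26/34 vs 16/34, p = 0.013 (chi-square) or 0.024 (Fisher), and fails the rule.

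**Sensitivity to the analysis set.** Section 10.1.5 limits the analysis for the study objective to subjects with at least 75% adherence, which conflicts with section 10.1.3. With 14 per arm, 50% vs 70% is non-significant in 86% to 90% of trials.

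**The case against.** The strongest reply is context. Section 2.2.4 says the two formulations are identical and differ only in presentation, and the trial is phase I and small by intent. A true rate of 80% or 90% against 50% is not the expected case. The planned summaries would show 76% against 47% to any reader, and the clinical part of the rule could block the conclusion. The 77% to 86% concerns one test, not the whole criterion, and the worked example fails the rule if eyes are the unit.

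Part of this stands. The single-test figures are upper bounds, the example holds at subject level only, and the three-test figures depend on assumed distributions. The most natural reading of the sentence is that neither kind of difference may be present, although it does not say so.

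None of it repairs the rule. Identical composition is a prior expectation, whereas the trial is meant to document the safety profile of the multi-dose product. The rule cannot tell agreement from lack of information. A clinical safeguard without a threshold cannot be applied reproducibly. If the study is exploratory, a categorical verdict is out of place.

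**Conclusion.** The concern holds and must be fixed, because following section 10.1.5 exactly can produce an unsupported headline conclusion. At subject level, with 17 per arm and a comparator incidence near 50%, a true 20-point AE excess passes the AE present/absent test in 77% to 86% of trials and a 30-point excess in 55% to 68%. Requiring all three primary tests lowers the 20-point figure to 71% to 76% with identical ICO, or 53% to 57% with a 0.5 SD ICO difference, under the simulation assumptions given. Treating eyes as independent lowers the single-test figures but does not remove the problem, and the adherence-restricted set makes it worse. The finding that the rule lacks a margin, an interval, a clinical threshold and any efficacy endpoint rests on the text alone and needs none of these assumptions.

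**What to change.** Replace the decision sentence in section 10.1.5 with wording such as: *For each primary outcome the between-group difference (multi-dose minus single-dose) will be reported with a two-sided 95% confidence interval: subject-level AE risk difference, AEs per subject, and day-8 ICO. A non-significant p-value will not be taken as evidence of similarity.* Name one interval method per outcome in advance, for example Newcombe or Miettinen-Nurminen for the risk difference. Delete the claim of effectiveness.

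Allow a non-inferiority claim only for an outcome whose margin is stated and justified beforehand, and only if the upper limit of that interval (or of one at another single pre-stated level) lies below the margin. The 5% margin is for a proportion and cannot be carried over to ICO.

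Align sections 1.1, 2.3.4, 7.3.3 (Table 2), 10.1.2 and 10.2.2 with the framework kept, and state which analysis set and unit apply. If the framework is descriptive, justify n = 34 by precision: a 95% half-width of about 30 to 34 points for the AE risk difference when incidence is near 50%.

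**Cost.** The change needs rewording and intervals on outcomes already collected, with no new subjects or procedures. It alters the hypotheses and the decision rule, so it needs an amendment with the committee review and COFEPRIS authorization described in section 11.2. The sponsor also loses the option of declaring similarity from p > 0.05. A 5-point non-inferiority claim is out of reach at this size. With 50% in both arms and 17 per arm, power is about 5% to 6% using the two-sided 95% limit, and 80% power needs 0.5 × (1.960 + 0.842)² / 0.05² = 1,569.8 (with unrounded z), so 1,570 per arm. At one-sided 0.05, power is about 9% to 11% and the requirement is the 1,237 per arm shown above.

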#### 2.4.2 Known potential benefits

As they are healthy subjects, no potential benefits for the subjects are expected. An improvement in eye comfort may occur, however, it may not be significant.

The benefits of the study will be to document the safety profile of Lagricel® Ofteno multi-dose.

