#### 2.6 Justification

Patients with dry eye, regardless of its etiology and degree of severity, will have to use ocular lubricants to reduce symptoms and improve their quality of life.

Ocular lubricants constitute the first line of treatment for ocular symptoms related to dry eye in healthy referring subjects, with a prevalence of 5 to 35% in those older than 50 years. [26] If we add to this those who report occasional symptoms or that depend on some work or occupational situation and who will use it for intermittent periods throughout their lives, the spectrum of the population that will have access to these drugs is very extensive. It is estimated that 50% of patients diagnosed with dry eye without concomitant diseases will use more than 2 types of ophthalmic solutions in 5 years of treatment.

For this reason, preservative-free lubricants have gained importance, to reduce the deleterious effect of the accumulated dose of preservatives. One of the disadvantages of preservative-free

Study No: SOPH037-0119/I

Version 1.0 31-January - 2019

ophthalmic products is the single-dose presentation, which makes the treatment more expensive for various reasons, including the loss of the product. With the development of new technologies, it has been possible to create a new generation of preservative-free products in multi-dose presentation.

Lagricel® Ofteno multi-dose is a preservative-free lubricant in multi-dose presentation which requires documentation of its safety and efficacy profile.

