## 2.3 Objectives and Hypotheses

#### 2.3.1 Primary objectives

To evaluate the safety and tolerability of the multi-dose Lagricel® Ofteno formulation manufactured by Sophia Laboratories S.A. of C.V. on the ocular surface of clinically healthy subjects.

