#### 2.3.2 Specific objectives

- Compare the safety of the Lagricel® Ofteno multi-dose formulation against Lagricel®
   Ofteno unit doses manufactured by Sophia Laboratories S.A. of C.V. through the incidence
   of AD.
- Compare the tolerability of the Lagricel® Ofteno multi-dose formulation against Lagricel®
   Ofteno unit-dose manufactured by Sophia Laboratories S.A. of C.V. using the ICO score.

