#### 2.4.2 Justification of the study design

The study design (clinical trial) is considered the highest quality standard in data when looking to explore the effect of an intervention. The drug development phase (phase I) corresponds to the objective of the study, which is to evaluate safety and tolerability, so the intervention time is short and the required sample size is smaller than that of a clinical efficacy trial. The presence of parallel groups allows comparison between the intervention groups on the outcome variables. Blinding was not considered for this study due to the characteristics of both investigational products.

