For this study, it will be considered that a minimum adherence of 70% is what is necessary to meet the research objectives. Therefore, subjects who present an adherence of less than 70% will not be considered for the efficacy analysis, they will only enter the safety analysis.

Study No: SOPH037-0119/I Version 1.0 31-January - 2019

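### The conclusion rule in 10.1.5 declares the product effective, but every objective is safety or tolerability and no outcome is designated as efficacy, so the trial's own data cannot support that word

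*Combined protocol and SAP*

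**What the plan says.** The rule is in 10.1.5 (Subjects included in the analysis): "The investigational drug will be considered safe and effective" if every primary outcome shows neither a clinical nor a statistical difference from the single-dose comparator. Just before it, the same section restricts the analysis that serves the study objective to subjects with at least 75% adherence by diary.

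The purpose of the trial is stated differently elsewhere:

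- 2.3.1 (Primary objectives): "To evaluate the safety and tolerability of the multi-dose Lagricel® Ofteno formulation".
- 2.3.2 (Specific objectives): AE incidence serves the safety comparison. ICO serves the other one: "Compare the tolerability of the Lagricel® Ofteno multi-dose formulation".
- 2.3.3 and 2.3.4: all five secondary objectives are safety comparisons, and both hypotheses are about the safety and tolerability profile.
- 2.4.2 (Justification of the study design): the phase I label is said to match the study's aim, "which is to evaluate safety and tolerability, so the intervention time is short". The same sentence calls the sample smaller than an efficacy trial would need.
- 2.4.2 (Known potential benefits): "As they are healthy subjects, no potential benefits for the subjects are expected". The next sentence allows that eye comfort may improve, perhaps not significantly.

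Efficacy appears operationally in one other place. Section 6.4 says that subjects below 70% adherence "will not be considered for the efficacy analysis, they will only enter the safety analysis". No section defines that efficacy analysis.

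**The concern.** A pre-specified conclusion rule should follow from what the trial measures. Here one word goes further than the objectives, hypotheses, outcomes, population and design rationale. Followed as written, the rule lets a trial of safety and tolerability in healthy volunteers yield a finding of effectiveness. Section 2.3.1 (From the research question) says there is no earlier clinical information on the multi-dose product, so this trial would be its first. Section 13.2 sends the final report to the regulator and both committees.

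The undefined efficacy analysis in 6.4 has a practical effect of its own. That section sorts low-adherence subjects into safety only, and ICO is named as neither safety nor efficacy. A reader cannot tell whether this primary outcome is analysed in adherent subjects or in everyone exposed.

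**Working it through.** The plan gives no figure to reproduce on this point. The check sets the rule against the rest of the document, with two short calculations.

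**1. Objectives.** 1 primary (2.3.1) + 2 specific (2.3.2) + 5 secondary (2.3.3) = 8. Concerning efficacy: 0 of 8. The hypotheses in 2.3.4 add none.

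**2. Outcomes.** 2 primary (7.3.1: AE incidence, ICO) + 5 secondary (7.3.2: visual acuity, two stainings, hyperemia, chemosis) = 7. Designated as efficacy: 0 of 7. AE incidence and the five secondary outcomes are tied to safety by 2.3.2 and 2.3.3, and ICO to tolerability by 2.3.2.

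**3. Population and sample size.** Section 2.5.1.1 requires clinically healthy subjects, while the synopsis gives dry eye as the use. The rates used in 10.2.2 are AE rates from a phase I lubricant study in healthy subjects. No efficacy quantity enters the sample size. Whether that calculation is right is a separate matter.

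**4. What the rule can show.** It is met when the two arms look alike on AEs and ICO. There is no untreated or placebo arm, and no benefit is expected in these subjects. Similar ICO scores would be seen if both products relieved symptoms and also if neither did. Similarity therefore does not separate *effective* from *not effective*. A better test or a larger sample would not change this.

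**5. How readily the AE part is met.** Take 17 subjects per arm and the plan's 50% AE rate on the comparator. Let x and y be the numbers of subjects with an AE on the multi-dose and single-dose products, and p the true multi-dose rate. The chance of no significant difference is the sum, over all x and y with a two-sided P value above 0.05, of Bin(x; 17, p) × Bin(y; 17, 0.5).

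| True multi-dose rate | Fisher throughout | Chi-square, or Fisher if an expected count is below 5 (10.1.2) |
|---|---|---|
| 50% | 0.98 | 0.94 |
| 60% | 0.95 | 0.90 |
| 70% | 0.86 | 0.77 |
| 80% | 0.68 | 0.55 |

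This covers the AE outcome only. The rule also needs ICO and an undefined absence of clinical difference. The table shows that the rule can be met when the arms truly differ in safety. That is a separate defect, and the present point does not rest on it.

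**6. Adherence thresholds.** Four applications a day for 7 days give 4 × 7 = 28 occasions. Under 6.4, 0.70 × 28 = 19.6, so 20 recorded occasions suffice. Under 10.1.5, 0.75 × 28 = 21 are needed. A subject with 20 of 28 (71.4%) is in under one section and out under the other. By contrast, 10.1.3 takes everyone exposed at least once into the safety evaluation.

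**The case against.** The strongest reply is that the claim is relative to a known product. Section 2.2.4 says the two formulations are identical, 2.6.1.1 and 2.6.1.2 list the same active concentration and excipients, and 2.6.1.2.1 says the comparator's safety and efficacy profile is already described. The sponsor could argue that efficacy carries over. That stands as a possible argument, and it means the product may well be effective. But it would rest on pharmaceutical sameness and earlier studies. The rule in 10.1.5 does not appeal to either: it derives *effective* from this trial's primary outcomes.

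Second, ICO is a symptom score (7.3.3.2, annex 15.1), comfort may improve, and 10.1.2 plans within-group tests. It is fair to say that a symptom score could serve as an efficacy measure elsewhere, so the count of 0 of 7 depends partly on the role the plan gives it. Here that role is tolerability, and the rule uses the comparison between arms.

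Third, the word may be loose drafting that the title and objectives put in context. Perhaps so, but 6.4 uses efficacy operationally too, and 10.1.5 is where the conclusion is fixed.

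A reader might infer more than the documents support:

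- *That the claim would be false whatever the data show.* It would be unsupported, which is different.
- *That the subjects have no dry eye to improve.* Eligibility requires clinical health but neither names dry eye as an exclusion nor sets a symptom or staining limit. The text supports only that subjects are not enrolled for dry eye.
- *That the final report will call the product effective.* Sections 13.1 and 13.2 say only that a report will be written and shared.
- *That 2.6 (Justification) makes the same error.* Its statement that the product "requires documentation of its safety and efficacy profile" describes what the product needs, not what this trial concludes.

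**Conclusion.** The point holds as an inconsistency between the conclusion rule and the rest of the plan. No objective (0 of 8) and no outcome (0 of 7) is designated as efficacy, and the subjects are healthy, so the trial's data cannot support *effective*. The finding rests on the roles the plan itself gives its outcomes, chiefly ICO as tolerability, and on no numerical assumption.

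It does not show that the product lacks efficacy, and it is not a flaw in the choice of a phase I design. The wording in 10.1.5 is wrong as written and should be corrected before the rule is applied. The related gap in 6.4, an efficacy analysis without an outcome and a 70% against 75% threshold conflict, should be closed at the same time because it leaves the ICO analysis set undefined.

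**What to change.** **10.1.5.** Delete *and effective*. Limit the conclusion to safety and tolerability relative to the single-dose product, over 7 days, in clinically healthy subjects.

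**6.4 and 10.1.5 together.** Remove the reference to an efficacy analysis, and reconcile the 70% and 75% thresholds so that one value defines one adherence-restricted set. Analyse AE incidence and ICO in all exposed subjects, with the adherence-restricted set as supportive. Merely renaming the efficacy analysis a tolerability analysis would be worse: it would fix in place the removal of low-adherence subjects from the ICO comparison, and those who stop the drops because of discomfort are the ones a tolerability comparison must keep. Exposed subjects without a day 8 ICO score should be counted and reported by arm.

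2.6 (Justification) needs no change.

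**Cost.** The 10.1.5 change is wording only, and the sponsor gives up a claim that this trial cannot support. The analysis-set change adds one supportive analysis. Subjects, visits, procedures and sample size stay as they are. The rule's reliance on finding no difference needs its own correction, which this edit does not supply.
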